4.1 Rationale

The rationale for this open label, switch over study is based on the enhanced PK profile of pegunigalsidase alfa. Phase 1/2 study measurements and PK projection modelling data suggest pegunigalsidase alfa 2.0 mg/kg every 4 weeks would be beneficial in patients with Fabry Disease currently treated with ERT.

The weekly projected partial AUC and average concentration (C_{ave}) indicate that there should be measurable levels of pegunigalsidase alfa at the third and fourth weeks after infusion in the same order of magnitude as Fabrazyme® in the first week after infusion ([Table 1:](#)). Calculations enabled the evaluation/estimation of the drug availability on weeks 1, 2, 3, and 4 of pegunigalsidase alfa compared to Fabrazyme® every other week following repeated dosing. The half-life (t_{1/2}) of 2.0 mg/kg pegunigalsidase alfa is ~ 80 hrs vs. ~2 hrs of Fabrazyme® and Replagal™ with C_{max} values ~10x greater than those published for Fabrazyme® (Fabrazyme® USPI 2016). The estimated C_{ave} of 2.0 mg/kg pegunigalsidase alfa every 4 weeks provides a concentration of ~90 ng/mL at the 3rd week and ~10 ng/mL at the 4th week post infusion. Both values are greater than the negligible 2nd week C_{ave} values for Fabrazyme® ([Table 1:](#)).

Table 1: Partial AUC/ C_{ave} (by Week) – Modeling Based on Pegunigalsidase alfa Phase 1/2 Data and Fabrazyme® AUC ~700 $\mu\text{g}\cdot\text{min}/\text{mL}$

| Time (week) | pegunigalsidase alfa 2 mg/kg | | | Fabrazyme® 1 mg/kg | | |
|----------------|------------------------------|------------------|------------------|--------------------|------------------|------|
| | IV every 2 weeks | IV every 4 weeks | IV every 2 weeks | IV every 2 weeks | IV every 2 weeks | |
| 1 | 989,406 | 5,889 | 989,406 | 5,889 | 12,000 | 71.4 |
| 2 | 119,065 | 709 | 119,065 | 709 | nil | nil |
| 3 | 1,004,012 | 5,976 | 14,637 | 87 | 12,000 | 71.4 |
| 4 | 120,864 | 719 | 1,799 | 11 | nil | nil |
| 5 | 1,004,233 | 5,978 | 989,627 | 5,891 | 12,000 | 71.4 |
| 6 | 120,892 | 720 | 119,092 | 709 | nil | nil |
| 7 | 1,004,233 | 5,978 | 14,640 | 87 | 12,000 | 71.4 |
| 8 | 120,892 | 720 | 1,800 | 11 | nil | nil |
| 9 | 1,004,233 | 5,978 | 989,627 | 5,891 | 12,000 | 71.4 |
| 10 | 120,892 | 720 | 119,092 | 709 | nil | nil |
| 11 | 1,004,233 | 5,978 | 14,640 | 87 | 12,000 | 71.4 |
| 12 | 120,892 | 720 | 1,800 | 11 | nil | nil |

Note: Since the projection was done for repeated dosing, the different shading indicates the infusion intervals to make it easier to follow.

This treatment dose and regimen is aimed as a maintenance program for Fabry patients without severe clinical symptoms with relatively slowing disease progression. Additionally, it may address the clinical needs of early or younger diagnosed patients.

The unique PK parameters of pegunigalsidase alfa with the proposed dose and regimen have the potential to results with a comparable efficacy and safety profile with a reduced immunogenicity compared to current ERTs, with greater convenience leading to significant improvement in QOL. This has the potential to delay the risk of developing disease complication in mild to moderate patients by slow disease progression. This study will provide health care providers and patients with Fabry disease alternative treatment options based on the unique characteristics of pegunigalsidase alfa.

5 STUDY OBJECTIVES

To evaluate the safety and efficacy of 2.0 mg/kg pegunigalsidase alfa every 4 weeks in patients with Fabry disease currently treated with ERT (agalsidase alfa or agalsidase beta).

6 INVESTIGATIONAL PLAN

6.1 Overall Study Design and Plan – Description

This will be an open-label, switch-over study to assess the safety and efficacy of pegunigalsidase alfa 2.0 mg/kg administered by intravenous infusion every 4 weeks for 12 months (52 weeks) in adult patients with Fabry disease currently treated with ERT: Fabrazyme® (agalsidase beta) or

Replagal™ (agalsidase alfa) for at least 3 years and on a stable dose (>80% labelled dose/kg) for at least the last 6 months.

Number of Subjects (Planned):

Up to 30 but not less than 25 of the enrolled patients, up to 6 of the patients will be females (~20%).

Following screening, patients will be enrolled and switched from their current ERT to receive intravenous (IV) infusions of pegunigalsidase alfa 2 mg/kg every 4 weeks for 52 weeks or 14 infusions.

At the time of enrollment, if premedication is used for the agalsidase alfa or agalsidase beta infusions before enrollment, this premedication will be continued through the first infusion with pegunigalsidase alfa and then gradually tapered down at the Investigator's discretion and based on [Appendix 8](#).

For patients weighing up to (\leq) 100 kg, the first infusions of pegunigalsidase alfa will be administered under controlled conditions at the investigation site starting at 4.5 hr with the option to reduce the IV duration gradually to 2 hr (see [Appendix 8](#)).

For patients weighing more than ($>$) 100 kg, the first infusions of pegunigalsidase alfa will be administered under controlled conditions at the investigation site starting at 6 hr with the option to reduce the IV duration gradually to 3 hr (see [Appendix 8](#)).

The first infusions of pegunigalsidase alfa will be administered under controlled conditions at the investigation site. The patient can receive their pegunigalsidase alfa infusions in a home care setup once the Investigator and Sponsor Medical Director/Monitor agree that it is safe to do so based on [Appendix 8](#).

In the case of clear clinical deterioration, the treatment may be changed to 1.0 mg/kg every other week at the Investigator's discretion and discussion with the Sponsor Medical Director/Monitor.

The study will include a screening visit and 14 treatment visits, once every 4 weeks for 52 weeks starting on Day 1 (Visit 1).

6.2 Discussion of Study Design

This study design is based on the unique enhanced PK profile of pegunigalsidase alfa. The weekly projected partial AUC and C_{ave} values, based on the Phase I/II PK profile, indicate that there should be measurable levels of pegunigalsidase alfa following 2 mg/kg treatment at the third and fourth weeks after infusion in the same order of magnitude as Fabrazyme® in the first week post-infusion ([Table 1](#):). Calculations enabled the evaluation/estimation of the drug availability on weeks 1, 2, 3, and 4 of pegunigalsidase alfa compared to Fabrazyme® every 2 weeks. The half-life ($t_{1/2}$) of 2.0 mg/kg pegunigalsidase alfa is ~ 80 hrs vs. ~2 hrs of Fabrazyme® and Replagal™ with C_{max} values ~10-fold higher than those found with Fabrazyme®. The estimated C_{ave} of 2.0 mg/kg pegunigalsidase alfa every 4 weeks provides an average concentration of ~90 ng/mL at 3 weeks and ~10 ng/mL at 4 weeks post infusion. Both are higher than the negligible 2nd week C_{ave} values for Fabrazyme® ([Table 1](#):).

Subjects are required to be treated with ERT: Fabrazyme® (agalsidase beta) or Replagal™ (agalsidase alfa) for at least 3 years and on a stable dose (>80% labelled dose/kg) for at least 6 months.

This study will provide a new treatment option based on the unique characteristic of pegunigalsidase alfa for health care providers and patients with Fabry disease in pegunigalsidase alfa-treated patients.

6.3 Selection of Study Population

6.3.1 Inclusion Criteria

The subjects must fulfill the following inclusion criteria:

1. Age: 18 – 60 years
2. A documented diagnosis of Fabry disease.
3. Males: plasma and/or leucocyte alpha-Galactosidase-A activity (by activity assay) less than lower limit of normal per laboratory reference range and one or more of the characteristic features of Fabry disease
 - a. Neuropathic pain
 - b. Cornea verticillata
 - c. Clustered angiokeratoma
4. Females: historical genetic test results consistent with Fabry mutations, or in the case of novel mutations a first-degree male relative with Fabry disease, and one or more of the characteristic features of Fabry disease
 - d. Neuropathic pain
 - e. Cornea verticillata
 - f. Clustered angiokeratoma
5. Treatment with agalsidase alfa or agalsidase beta for at least 3 years and on a stable dose (>80% labelled dose/kg) for at least the last 6 months
6. eGFR ≥ 30 mL/min/1.73 m² by CKD-EPI equation at screening visit
7. Availability of at least 3 historical serum creatinine evaluations since starting agalsidase alfa or agalsidase beta treatment and not more than 2 years
8. Female patients and male patients whose co-partners are of child-bearing potential agree to use a medically accepted, highly effective method of contraception. These include combined (estrogen- and progestogen-containing) hormonal contraception associated with inhibition of ovulation (oral, intravaginal, or transdermal), progestogen-only hormonal contraception associated with inhibition of ovulation (oral, injectable, or implantable), intrauterine device (IUD), intrauterine hormone-releasing system (IUS), bilateral tubal occlusion, vasectomised partner, or sexual abstinence

9. Patients whose clinical condition, in the opinion of the Investigator, that are suitable for treatment with ERT every 4 weeks.

6.3.2 Exclusion Criteria

The presence of any of the following excludes a subject from study enrollment:

1. History of anaphylaxis or Type 1 hypersensitivity reaction to agalsidase alfa or agalsidase beta
2. History of renal dialysis or transplantation
3. Linear negative slope of eGFR of ≥ 2 mL/min/1.73 m² based on at least 4 serum creatinine values over approximately 2 years (including the value obtained at the screening visit)
4. History of acute kidney injury in the 12 months prior to screening, including specific kidney diseases (e.g., acute interstitial nephritis, acute glomerular and vasculitic renal diseases); non-specific conditions (e.g., ischemia, toxic injury); as well as extrarenal pathology (e.g., prerenal azotemia, and acute post renal obstructive nephropathy)
5. Angiotensin converting enzyme (ACE) inhibitor or angiotensin receptor blocker (ARB) therapy initiated or dose changed in the 4 weeks prior to screening
6. Urine protein to creatinine ratio (UPCR) at screening > 0.5 g/g or mg/mg or 500 mg/g and not treated with an ACE inhibitor or ARB
7. Females who are pregnant, planning to become pregnant during the study, or are breast feeding
8. Cardiovascular event (myocardial infarction, unstable angina) in the 6-month period before screening
9. Cerebrovascular event (stroke, transient ischemic attack) in the 6-month period before screening
10. Presence of any medical, emotional, behavioral, or psychological condition that, in the judgment of the Investigator and/or Medical Director, would interfere with the patient's compliance with the requirements of the study.

6.3.3 Removal of Subjects from Therapy or Assessment

Reasons for permanent discontinuation include the following:

- The subject experiences two or more Grade 3 toxicities or one or more Grade 4 toxicity considered by the Investigator to be associated with pegunigalsidase alfa ([CTCAE v. 4.03, 2010](#))
- The subject experiences progressive hypersensitivity or severe hypersensitivity that is not allayed with pre-treatment

- The subject requests to discontinue treatment
- Investigator feels that it is not in the best interest of the subject to continue treatment and/or if the Investigator believes that the subject can no longer be compliant with the requirements of the study

For any discontinuation, the Investigator will obtain all the required details and document the date and the main reason for the premature termination. If the reason for discontinuation is an adverse event, the specific event or the main laboratory abnormality will be recorded in the CRF. The Investigator will make thorough efforts to document the outcome. The Investigator will attempt to continue to follow the subject for the full duration of the study or at least for 30 days following discontinuation. If circumstances prevent the subject from completing all visits, every attempt will be made to complete all procedures listed in [Section 9.2.3](#) for Visit 14 excluding the drug infusion.

7 STUDY PRODUCT

7.1 Study Medication Supply

Protalix will provide pegunigalsidase alfa to the sites as needed.

7.2 Description and Formulation of Study Product

Pegunigalsidase alfa is a purified recombinant, plant cell-expressed chemically modified human alpha galactosidase A, which is described in detail in the Investigator's Brochure.

The Drug Product (DP) is provided in 15 ml clear glass vials closed with rubber stoppers and secured with aluminum flip off caps.

Each vial contains 10.5 mL of the following contents in liquid form:

20 mg pegunigalsidase alfa (2.0 mg/mL)
0.7% NaCl
25-30 mM Sodium Citrate (pH 5.7 – 6.3).

7.3 Study Drug Dosage and Preparation

Pegunigalsidase alfa 2.0 mg/kg; the individual dose for each patient will be prepared according to the patient's weight at screening. In the case of clinical deterioration, the treatment may be changed to 1.0 mg/kg every two weeks at the Investigator's discretion and discussion with the Medical Monitor.

Dose of PRX-102 will be adjusted at visit 8 if the weight at visit 7 changes by $\geq 25\%$ from screening weight

Each dose will be prepared by a pharmacist or nurse at each site. The required amount of enzyme will be adjusted with normal saline (0.9% NaCl) to a final volume of 150 mL/infusion for patients weighing at screening up to 70 kg, 250 mL/infusion for patients weighing between 70–

100 kg, and 500 mL/infusion for patients weighing more than 100 kg the volume will be adjusted only if dose is changed.

7.4 Study Drug Administration

For patients weighing up to (\leq) 100 kg, the first infusion of pegunigalsidase alfa will be administered under controlled conditions at the investigation site starting at 4.5 hrs with the option to reduce the IV duration gradually to 2 hrs.

For patients weighing more than ($>$) 100 kg, the first infusion of pegunigalsidase alfa will be administered under controlled conditions at the investigation site starting at 6 hrs with the option to reduce the IV duration gradually to 3 hrs.

Study drug will be administered by intravenous infusion over 4.5 – 6 hrs. If well tolerated by the patient, the infusion rate may be adjusted to 2 – 3 hrs ([Appendix 8](#)) according to the individual subject's signs and symptoms ([Appendix 2](#)). All changes will be based on Investigator evaluation and Sponsor Medical Director approval.

The first infusions of pegunigalsidase alfa will be administered under controlled conditions at the investigation site. After tapering down premedication, when applicable, and reducing the infusion time and observation time (see [Appendix 8](#)), the patient can then receive the pegunigalsidase alfa infusions at a home care setup once the Investigator and Sponsor Medical Director agree that it is safe to do so.

7.5 Packaging and Labeling

The DP is provided in 15 mL clear glass vials closed with rubber stoppers and secured with aluminum flip off caps. The drug product is packaged in vials containing 20 mg pegunigalsidase alfa (2 mg/mL), 0.7% NaCl, and 25 – 30 mM Sodium Citrate (pH 5.7 - 6.3).

Study product is a liquid stored in 15 mL clear injection glass vials (Müller + Müller-Joh. GmbH + Co, Germany). Grey rubber stoppers (formulation 4432/50/Grey) are used for closure (West Pharmaceutical Services Deutschland GmbH & Co KG).

The label is presented in [Appendix 1. Vial Label](#)

7.6 Conditions for Storage and Use

The proposed storage condition for the pegunigalsidase alfa DP is $5 \pm 3^{\circ}\text{C}$. The proposed storage condition for the infusion bag is $5 \pm 3^{\circ}\text{C}$, RT, and at $22.5 \pm 2.5^{\circ}\text{C}$ for up to 36 hours.

7.7 Method of Assigning Subjects Identification

In this open label study, all subjects will receive 2 mg/kg pegunigalsidase alfa once every 4 weeks:

A unique screening number (formatted as xxSF50yyy [x: site number, S: screening, F50: constant indicating protocol number, y: sequential subject number in the site]) will be assigned to each screened subject. Once a subject is eligible for treatment, including successful completion

of screening, sponsor medical director approval but prior to visit 1, a subject enrollment ID number will be generated. This ID number will include the site and subject number (formatted as xx-F50yyy [xx: site number, F50: constant indicating protocol number, yyy: sequential subject number in the study]).

7.8 Dispensing, Compliance and Accountability

Protalix will provide drug accountability forms to assist the pharmacist in maintaining current and accurate inventory records covering receipt, dispensing, and the return of investigational drug supplies. When a shipment is received, the pharmacist will verify the quantities received and return the acknowledgment to the Protalix's CTM (Clinical Trial Material) coordinator. The drug will not be used without Protalix's approval in writing. The pharmacist investigational drug accountability record includes the identification of the person to whom the drug is dispensed, the quantity and the date of dispensing and any returned or unused drug, as well as a full record of CTM storage temperatures. This record is in addition to any drug accountability information recorded on the Case Report Form (CRF). These records will be readily available for inspection by a monitor and/or Protalix audits and are open to regulatory authority inspection at any time.

The Investigator is responsible for maintaining accountability for the receipt, dispensing, and return of all study medication.

7.9 Prior and Concomitant Therapy

Medications having the potential to interfere with the evaluation of efficacy are excluded throughout the trial.

The following medications are strictly prohibited during the study:

- Fabrazyme® (agalsidase beta)
- Replagal™ (agalsidase alfa)
- Any other investigational or approved drug for treating Fabry disease.

Angiotensin-converting enzyme inhibitors (ACEIs) and angiotensin II receptor blockers (ARBs) at a stable dose for 4 weeks prior to entry into the study are allowed, but once a subject is randomized in the study, initiation of ACEI or ARB therapy is permitted only after discussion and approval of the Sponsor Medical Director.

8 EFFICACY AND SAFETY ASSESSMENTS

8.1 Efficacy Variables

- Estimated glomerular filtration rate (eGFR_{CKD-EPI}) ([Appendix 5. National Kidney Foundation Guidelines for Chronic Kidney Disease](#))
- Left Ventricular Mass Index (g/m²) by echocardiogram
- Plasma Lyso-Gb3
- Plasma Gb3

- Urine Lyso-Gb3
- Protein/Creatinine ratio spot urine test (UPCR)
- Frequency of pain medication use
- Exercise tolerance (Stress Test)
- Short Form Brief Pain Inventory (BPI) ([Appendix 7. Brief Pain Inventory- BPI \(Short Form\)](#))
- Mainz Severity Score Index (MSSI) ([Appendix 4. The Mainz Severity Score Index \(MSSI\)](#))
- Quality of life EQ-5D-5L ([Appendix 6. QOL Questionnaire - EQ-5D-5L](#))

8.2 Pharmacokinetic Variables

Blood samples will be taken from all patients for PK analysis on Day 1 and at the end of the study (Visit 14 at week 52). Blood samples will be drawn for an additional intermediate PK analysis at Visit 7 (week 24), for all patients who signed inform consent to this version (Version 4) before reaching Visit 7 (week 24), or at Visit 11 (week 40) for patients who passed Visit 7 at the time of signing the inform consent to this version. The following (but not restricted to) PK parameters will be derived from the plasma concentration versus time profiles to determine the pharmacokinetics of the study drug: C_{max} , T_{max} , $t_{1/2}$, AUC_{0-t} , and $AUC_{0-\infty}$. Blood samples (~6 mL) will be drawn at the following time points: pre-infusion (baseline); 1 hour after the beginning of the infusion; at the end of the infusion, at 1 ± 0.25 , 2 ± 0.25 , 4 ± 0.25 , 8 ± 0.25 , 24 ± 0.5 , 48 ± 3 , and 96 ± 3 hours post-infusion and at 14 ± 3 , 21 ± 3 and 28 ± 3 days post-infusion (a total of 13 timepoint within 28 days).

8.3 Safety Variables

Safety will be assessed by changes from baseline in:

- Clinical laboratory tests
- Physical examination
- Assessment of the injection site
- Electrocardiogram
- Treatment-emergent adverse events
- Ability to taper off infusion premedication throughout the first 2 months of the study
- Requirement for use of premedication overall to manage infusion reactions

- Treatment-induced anti-pegunigalsidase alfa antibodies ([Appendix 3. Pegunigalsidase alfa Hypersensitivity Evaluation and Treatment Algorithm](#))

8.3.1 Adverse Events

An adverse event (AE) is any untoward medical occurrence in a subject participating in a clinical trial. An AE can be any unfavorable and unintended sign, symptom, or disease temporally associated with the use of the study medication, whether or not considered related to the study medication. AEs will be collected from the start of treatment until 30 days following the final visit dose. If the subject enters the extension study, the first 30 days of the extension study will be considered the observation period for adverse events of this study (PB-102-F50). Any events occurring prior to treatment will be recorded on the medical history page with the event name and onset date and end date if not continuing. Known pre-existing clinically significant conditions observed at screening should be recorded as medical history.

This definition also includes accidental injuries, reasons for any change in medication (drug and/or dose) other than planned titration, reasons for admission to a hospital, or reasons for surgical procedures (unless for minor elective surgery for a pre-existing condition). It also includes AEs commonly observed and AEs anticipated based on the pharmacological effect of the study medication. Any laboratory abnormality assessed as clinically significant by the Investigator must be recorded as an AE.

A treatment-emergent AE is any AE occurring after start of study medication and within the time of residual drug effect (30 days after the last administration of the study medication; please note the above provision for subjects who enter the extension study), or a pre-treatment AE or pre-existing medical condition that worsens in intensity after start of study medication and within the time of residual drug effect.

AEs should be recorded as diagnoses, if available. If not, separate sign(s) and symptom(s) are recorded. One diagnosis/symptom should be entered per record. Treatment-related hypersensitivity/infusion reactions are defined in [Appendix 3. Pegunigalsidase alfa Hypersensitivity Evaluation and Treatment Algorithm](#) and can be defined as a single AE at the Investigator's discretion.

Note that death is not an event, but the cause of death is. An exception is the event of sudden death of unknown cause. Note that hospitalization is not an event; however, the reason for hospitalization is. Procedures are not events; the reasons for conducting the procedures are. In general, only the reason for conducting the procedure will be captured as an AE. However, if deemed necessary by the Investigator, a procedure can be captured along with the reason for conducting the procedure.

An overdose is not an AE unless it is temporally associated with an unfavorable or unintended sign or symptom.

Each AE is to be classified by the Investigator as serious or non-serious. A serious adverse event (SAE) is any untoward medical occurrence or effect that occurs at any dose:

- Results in death

- Is life-threatening (i.e., an immediate risk of death)
- Requires in-patient hospitalization or prolongation of existing hospitalization
- Results in persistent or significant disability/incapacity
- Is associated with a congenital anomaly/birth defect
- Is an important medical event

An AE caused by an overdose or medication error is considered serious if a criterion listed in the definition above is fulfilled.

Important AEs that may not result in death, may not be life-threatening, or do not require hospitalization may be considered serious when, based upon appropriate medical judgment, they may jeopardize the subject's safety or may require medical or surgical intervention to prevent one of the outcomes listed above.

SAEs also include any other event that the Investigator or sponsor judges to be serious or which is defined as serious by the regulatory agency.

The Investigator is to report all directly observed AEs and all AEs spontaneously reported by the trial subject using concise medical terminology. In addition, each trial subject will be questioned about AEs. The question asked will be "Since you began taking the study medication, have you had any health problems?"

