#### 10.2.2 Infusion Related Reactions (IRR)

IRRs are those TEAEs which occur during the infusion or within 2 hours after the completion of the infusion and their causality is definitely, probably, or possibly related.

Classification rules for assignment of patients with TEAEs during the infusion or within 2 hours after the infusion are described below.

Injection site reactions with SOC and PT listed in Table 2 are not considered IRR and should be excluded from the IRR analysis.

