**Table 2: Injection Site Reaction SOC and PT Not Considered as IRR**

MedDRA SOC	MedDRA Preferred Term
General disorders and administration site conditions	Infusion site discomfort Injection site discomfort Infusion site pain Injection site pain Infusion site hematoma Injection site hematoma
Injury poisoning and procedural complications	Contusion Procedural site reaction Procedural pain
Vascular disorders	Vein rupture

The number and percentage of patients with at least one IRR and the number of IRRs will be reported in an overall table with the following parameters: Any IRR; Mild or moderate IRRs; Severe IRRs; Serious IRRs; IRRs leading to withdrawal; IRRs leading to death.

This analysis will be repeated for the following sub-groups: ADA; Gender; Previous ERT; FD classification. An additional sub-group will be the location of administration (Home or Site).

IRR summary tables by SOC and PT will present the number and percentage of subjects with at least one IRR and the number of IRRs. The tables for the IRRs will be presented overall and by severity.

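### The planned number of IRRs is a count of AE records, so it can exceed the number of infusion reactions and depends on how investigators record them

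*Protocol*

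**What the plan says.** **Recording (Protocol 8.3.1).** The default is "AEs should be recorded as diagnoses, if available. If not, separate sign(s) and symptom(s) are recorded". It is followed by "One diagnosis/symptom should be entered per record". For treatment-related hypersensitivity or infusion reactions, which the protocol defines through Appendix 3, there is an option: the reaction "can be defined as a single AE at the Investigator's discretion". Nothing says when the option should be used.

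**Definition (SAP 10.2.2).** "IRRs are those TEAEs which occur during the infusion or within 2 hours after the completion of the infusion", provided that "their causality is definitely, probably, or possibly related". The only exclusion by term is that "Injection site reactions with SOC and PT listed in Table 2 are not considered IRR".

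**Reporting (SAP 10.2.2).** "The number and percentage of patients with at least one IRR and the number of IRRs will be reported in an overall table", with rows for severity, seriousness, withdrawal and death. The table is repeated by ADA status, gender, previous ERT, FD classification and location of administration (Tables 14.3.3.5.1 to 14.3.3.5.3). For Tables 14.3.3.6.1 and 14.3.3.6.2, "IRR summary tables by SOC and PT will present the number and percentage of subjects with at least one IRR and the number of IRRs".

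**Role of the analysis (SAP 12, items 1 and 8).** IRR was added as an endpoint, and hypersensitivity, which the protocol would have analysed as an AE of special interest, is to be evaluated within it.

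**The concern.** The protocol allows two ways to enter the same clinical reaction. An investigator who sees flushing, pruritus and chest discomfort during one infusion may enter one AE or three. The SAP carries whatever was entered straight into the IRR count. Two sites with the same experience can therefore contribute different numbers, and a reader who takes the number of IRRs to mean the number of reactions will be misled.

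The home/site split is the most exposed. Location belongs to the infusion, and one patient may have infusions in both places. SAP 10.1 reports the number of infusions by location, so a reader has a denominator and is likely to divide by it. The quotient would be AE records per infusion, not the share of infusions with a reaction. No planned table gives that share.

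**Working it through.** The plan states no IRR rate, event count or power figure on this point, so there is nothing of its own to reproduce. The check has three steps.

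**1. Is there a grouping rule?**
- SAP 10.2.2 applies its timing and causality criteria to each TEAE and stops there.
- The only collapsing rule found is in SAP 10.2.1. It takes the worst severity and closest relationship when a subject has the same PT more than once. It cannot merge different symptoms of one reaction, and it does not govern the number of events.
- SAP 7.1 was not in the text available for this review, and the table shells are a separate document (SAP 14). A counting convention there cannot be excluded.

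**2. What does the event count become?** Let R be the number of reactions, k the qualifying symptoms per reaction and s the share of reactions entered as separate symptoms. Then

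IRR count = R(1 − s) + R·s·k, and count ÷ reactions = 1 + s(k − 1).

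From the documents: 30 patients (SAP 4.1) and 14 planned infusions each (Protocol synopsis), so 30 × 14 = 420 planned infusions. Actual infusions will differ with early termination or a change of regimen.

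Assumed, because the documents give no values: R = 10, and k = 2, 3 or 5. The five signs listed as moderate in Protocol Appendix 3 show that a reaction with several signs is foreseen.

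| Share split (s) | k = 2 | k = 3 | k = 5 |
|---|---|---|---|
| 0 | 10 | 10 | 10 |
| 0.5 | 15 | 20 | 30 |
| 1 | 20 | 30 | 50 |

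For example, s = 0.5 and k = 3 gives 10 × 0.5 + 10 × 0.5 × 3 = 20. Divided by 420 planned infusions, the corners are 10/420 = 2.4, 20/420 = 4.8, 30/420 = 7.1 and 50/420 = 11.9 per 100 infusions. The SAP plans no such rate; this is what a reader would get by dividing. The ratio to true reactions does not depend on R. It runs from 1 (all merged) to 5 (all split with five symptoms).

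**3. Which patient counts move?** Take one patient with one reaction made up of one severe and two mild symptoms, all related and in the window.

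| Patient count | One AE record | Three AE records |
|---|---|---|
| Any IRR | 1 | 1 |
| Severe IRR | 1 | 1 |
| Mild or moderate IRR | 0 | 1 |
| PTs in which the patient appears | 1 | 3 |

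The any-IRR row is stable as long as the single record, and at least one of the split records, meets the window and causality criteria. The mild-or-moderate row and the PT-level patient counts are not stable.

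**The case against.** Four points can be made for the plan.

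- **The SAP is open about its unit.** It says that IRRs are TEAEs and counts them as it counts all TEAEs. This stands. A reader might infer that protocol and SAP contradict each other, but they do not. The protocol governs data entry and the SAP counts entries. The weakness is that the resulting count is easily read as a number of reactions.
- **Variation in recording is bounded.** Diagnosis comes first and separate symptoms are the fallback, so the single-AE option largely extends the default. Only related, in-window AEs outside Table 2 count. This limits the effect without removing it, because no criterion for merging is given.
- **No formal comparison is at stake.** SAP 7.4 plans no tests, SAP 10.2.2 plans no interval or difference for IRRs, and SAP 7.5 allows a subgroup to be skipped if a group has fewer than 5 patients. A reader might infer that subgroup or home/site comparisons are biased. That would require recording style to differ between the groups, and nothing in the documents shows it.
- **The listings allow a hand count.** Listing 16.3.2.4 covers IRRs, and the TEAE listing carries onset and end dates. In 30 patients a diligent reader could group the records. This reduces the harm but does not replace a tabulated result.

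Nor do the documents rank IRR as the main safety result: it is one of nine unranked safety endpoints in SAP 3.2.1.

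**Conclusion.** The point holds for the event column of Tables 14.3.3.5.1 to 14.3.3.5.3, including the home/site split. That column counts AE records and can exceed the number of infusion reactions. The headline percentage of patients with any IRR is essentially safe. Patient counts by PT, and in the mild-or-moderate row, can shift with recording style.

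The size of the excess is unknown. The 10-to-50 range above rests on an assumed 10 reactions, assumed numbers of symptoms, and the extremes of all merged and all split. It shows how sensitive the count is and does not predict inflation. A reader might infer that IRR counts in this trial are inflated several-fold, but the documents give no rate, no symptoms per reaction and no sign of how often reactions were split.

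The conclusion also assumes that SAP 7.1 and the shells contain no grouping rule. It is a moderate point: a safety count with an ambiguous meaning that is cheap to clarify.

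**What to change.** In SAP 10.2.2:

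1. Add to the overall IRR tables, and to the home/site split, the number and percentage of infusions with at least one IRR. Use as denominator the partial or complete infusions already summarised in SAP 10.1. For each such infusion, take the highest severity and seriousness among the qualifying TEAEs linked to it. This result is the same whether a reaction was entered as one record or several.
2. Label the existing event count as IRR AE records. Add a footnote to the SOC/PT tables that one reaction may appear under several PTs.
3. State the link. Assign each AE to an infusion by onset date and time or, where these are incomplete, by question 1 of the drug administration form. List any AE that cannot be assigned.

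**Cost.** SAP wording, one grouping step and an extra row per severity or seriousness line. AE recording does not change and no new data are needed, since the timing rule in SAP 10.2.2 already uses both forms.

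**Downsides.** Two separate reactions at one infusion count once, which is possible because Protocol Appendix 3 foresees continuing the drug after symptoms resolve within a visit. The AE-record count and the PT tables should therefore stay alongside. The change does not make PT-level patient counts independent of recording style; the footnote only warns the reader. Question 1 is answered per infusion, so a few AEs with incomplete onset dates may remain unlinked.
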